**PI: [name].**

**NCT 02607046**

**Approval: March, 28, 2019**

## **Post-revascularization rehabilitation to improve function in Veterans with peripheral arterial disease (PAD)**

### STUDY PROCEDURES:

#### **INTERVENTIONS**

1. **Active Exercise Training:** All participants who are in the exercise program will exercise for approximately 3 months, 3 times per week at the Baltimore VA Medical Center Annex, or the VA Medical Center. These exercise sessions will be supervised by exercise physiologists or trained staff. The aerobic exercise training program will include a warm up followed by 30-45 minutes of cumulative walking on a treadmill or around a track. Individuals will initially begin walking for 10-15 minutes per exercise session (depending on tolerance) and will progress weekly until 30-45 minutes of cumulative walking has been achieved. For individuals who experience claudication pain, they will be asked to walk until the claudication pain reaches a 3 on a 0-4 scale (0= no pain, 1 = onset of pain, 2 = moderate pain, 3 = intense pain, and 4 = maximal pain) after which they will rest. They will then be asked to walk again. This pattern of intermittent walking will be continued until the prescribed number of minutes of walking is met. Subjects will also be asked to walk at home on days they do not perform supervised exercise. Participants may also participate in strength training (ST) during the same session. This will consist of training of the knee extensors, knee flexors, plantar flexors and dorsiflexors. Subjects will perform approximately 1-3 sets of 4-15 repetitions for each exercise as tolerated. Training may be performed on Keiser K-300 air powered machines utilizing pneumatic resistance (Leg Extension Machine, Leg Curl Machine, Leg Press Machine) or with resistance bands or tubes. Each session of ST will take approximately 15-30 minutes. Blood pressure and heart rate will be assessed before and after each session. If the participant has type 2 diabetes and is on medications that may result in hypoglycemia, we will monitor blood glucose levels before and after exercise.

2. **Passive Exercise Training (NMES):** Neuromuscular electrical stimulation (NMES) will be used to electrically induce contraction of the plantarflexors and dorsiflexors of both lower extremities. The protocol will employ an FDA cleared device for this purpose. NMES is routinely used in clinical care and has been used in other studies at UMB. Our specific protocol will require the application of NMES units on each lower extremity. Electrodes will be placed over the plantar and dorsiflexors of each leg. The stimulator's parameters setting will be adjusted to elicit contraction while maintaining participant comfort. Stimulation will be provided for approximately 15-30 minutes daily as tolerated by the participant.

#### **TESTING PROCEDURES:**

\*Based on each subject's schedule and availability, the Principal Investigator or clinical investigative team may choose not to perform every research procedure described below. If this occurs it will be noted in the participant research notes. Participants may also be asked to repeat one or more of the research tests should it be necessary due to a technical error in its performance and/or measurement, an inadequate sample is obtained for analysis, or there was an unforeseen problem with data collection.

1. **Blood Sampling:** Blood plasma and/or serum will be used to measure cardio-metabolic and angiogenic factors (growth factors, inflammatory cytokines, cardio- metabolic risk factors, and markers of nutritional status). We may also measure endothelial progenitor cells, new hormones, inflammatory proteins and biomarkers as other technologies for measuring biomarkers of cardiovascular disease are identified. We will store plasma and serum and blood

cells for analysis at a later time. These samples will be de-identified. Genetic testing will also be performed on blood samples.

2. Treadmill Exercise Test: The tests described below will be supervised by staff clinicians with the assistance of CPR-trained study team members. Subjects will walk on a treadmill at approximately 2mph and grade is increased every 2 minutes until the subject cannot continue. Subjects will wear a mask with a mouthpiece that will collect expired air for measurement of ventilated gasses. Subjects are instructed to report the onset of claudication pain and then to walk as long as they can endure the pain (at which time the test will end). Heart rate and ECG are monitored continuously; arm and ankle blood pressure is monitored intermittently throughout the protocol using either auscultation or Doppler ultrasound. Cardiac output (PhysioFlow Enduro) and calf muscle oxygen saturation (Oxiplex TS near-infrared spectroscopy) may also be non-invasively measured during the test. Exercise tests may be stopped if the subjects indicate they are unable to continue or they experience any of the following: chest pain, dizziness, faintness, fatigue, pallor, cyanosis, cardiac arrhythmias or decompensation, or severe hyper- or hypotension (American College of Sports Medicine 2006. Guidelines for Exercise Testing and Prescription 7th ed.). Subjects may be asked to repeat this test while wearing a NMES unit. During Phase 3 & 5 this test will be performed twice. Once to establish any improvements in how long the patient can walk they will be asked to walk as long as possible. The second test will be submaximal and will be terminated when the patient reaches the same time and grade completed in a previous research testing phase. The submaximal test will be supervised by a CPR-trained exercise physiologist.

3. Strength Testing: A) Muscular strength (leg extension, leg press, and/or leg flexion) will be measured by 1-repetition maximum (1RM) testing on Keiser K-300 air powered machines or a Biodex strength testing system. Participants will complete a brief, low-intensity warm-up prior to the test. Participants will be asked to perform exercises against a gradually increasing resistance after each successful exercise repetition until the maximal load is obtained. They will be perform multiple trials (typically ~3-7) with ~ 1 minute of rest between trials. B) Plantar and dorsiflexion will be measured using a hand-held dynamometer or with the Biodex strength testing system. Participants will be properly stabilized to ensure minimal movement artifacts. Additionally, verbal encouragement will be provided during task to encourage maximal volitional contraction.

5. Functional Tests and Questionnaires: The physical performance tests include the Modified Physical Performance Test [standing balance, chair rise, book lift, put on and remove jacket, pick up a penny, turn 360 degrees, 50-foot walk, stair ascent/descent, self-selected gait speed (8-foot walk)], grip strength, balance, and the 6-minute walk. We will also administer questionnaires (attached) including the Walking Impairment Questionnaire (WIQ), SF-36, the Life Space Questionnaire, and the Vascular Quality of Life (VascuQoL). Participants may be asked to repeat these tests while participating in the intervention so that we may assess interim efficacy.

6. Body Composition: Total and regional fat mass, lean tissue mass, % body fat, bone mineral content, and bone density will be determined by dual-energy x-ray absorptiometry (DXA). Computed tomography scans of the abdomen and leg are done to quantify regional fat and muscle distribution. The DXA and CT scans are performed by radiology technicians. [\*DXA and CT scans will only be performed during post-revascularization testing (Phase 3) and 3-month testing (Phase 5).] We will also measure body circumferences with a tape measure.

7.       Ultrasound Testing: This test may be performed before and after exercise. Doppler ultrasound non-invasively visualizes anatomic structures and determines intra- arterial blood flow. The test may be performed at the Vascular Laboratory at the University of Maryland Medical Center. Subjects will be positioned on a cushioned table and gel will be applied to their skin. An ultrasound transducer will be moved over the areas of the body being imaged. Contrast-enhanced ultrasonography will be employed to improve visualization. This involves the administration of stabilized microbubbles, an ultrasound contrast agent via a peripheral intravenous line. Participants will undergo the ultrasound testing before and after a walking on a treadmill for approximately 10 minutes.

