#### STATISTICAL ANALYSIS:

We will use exploratory data analyses to review our data looking for extreme values which will be checked for transcription or other errors. Because our outcome measures will be measured multiple times, our intent is to use repeated measures ANOVA to compare outcome measures among treatment and control. However, as this is a pilot study designed to demonstrate proof of concept and to generate data with which to make accurate power calculations, we may initially analyze within-group changes using paired t-tests and among-group differences with independent samples t-tests.

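### Tests may be skipped for scheduling reasons, but the analysis has no rule for partly observed participants, so classical repeated measures ANOVA or paired t-tests would discard data already collected

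*Combined protocol and SAP*

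**What the plan says.** The opening note of TESTING PROCEDURES makes every listed test optional at the team's discretion: "the Principal Investigator or clinical investigative team may choose not to perform every research procedure described below". The stated ground is the participant's "schedule and availability". The stated consequence is a record: "If this occurs it will be noted in the participant research notes". Repeat testing is offered for technical errors, inadequate samples and data-collection problems; it is not described as a remedy for a test skipped for scheduling reasons.

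STATISTICAL ANALYSIS starts from complete series, "Because our outcome measures will be measured multiple times", and continues "our intent is to use repeated measures ANOVA to compare outcome measures among treatment and control". It adds that "we may initially analyze within-group changes using paired t-tests and among-group differences with independent samples t-tests". Its only data-handling step is a check for extreme values and errors. It gives no analysis set, no missing-data method and no list of the phases that enter for each outcome.

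The number of phases differs by outcome. Body Composition (item 6) restricts DXA and CT to Phases 3 and 5. For the treadmill (item 2), "During Phase 3 & 5 this test will be performed twice", and the submaximal version stops at the level reached in an earlier testing phase. At least one treadmill test therefore precedes Phase 3, although nothing says that it enters the group comparison.

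**The concern.** The protocol creates partly observed participants by design, and the named methods, in their usual form, cannot use them. Classical repeated measures ANOVA needs a value at every phase entered. A paired t-test needs both visits. An independent samples t-test at one visit keeps everyone measured at that visit, but applied to change scores it loses the same people as the paired test.

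The stake is precision. The section says that "this is a pilot study designed to demonstrate proof of concept and to generate data with which to make accurate power calculations", and estimates of variance and change meant for later power calculations become less precise when measurements already taken are left out. A second, conditional stake is bias: if the people whose tests are skipped differ in function, and differ in a different way between groups, the comparison is distorted.

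**Working it through.** The plan states no figure that could be reproduced: there is no sample size, SD, skip rate or correlation. What follows is an illustration under assumptions.

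**Inputs, all assumed.** Chance p that a test is skipped at a visit: 10% or 20%, independent across visits. Correlation r between any two visits: 0.7, with 0.5 to 0.8 as range. Phases entering, k: two (as for DXA and CT) or three (possible for the treadmill).

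**Step 1: complete cases.** The share kept is (1−p)^k.
- p = 0.2: 0.8² = 0.640; 0.8³ = 0.512.
- p = 0.1: 0.9² = 0.810; 0.9³ = 0.729.

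A paired t-test on Phases 3 and 5 keeps the two-visit share (64% or 81%) however many phases exist.

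**Step 2: mixed model using all available values.** The effective share for the Phase 3-to-5 change is the variance with full data divided by the variance with skipped tests. Summing the information over all missingness patterns, with equal variances and correlations, gives:
- k = 2: (1−p)² + p(1−p)(1−r)
- k = 3: (1−p)² + p(1−p)²/(1+r) + p²(1−p)(1−r)

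At r = 0.7:
- p = 0.2, k = 2: 0.640 + 0.16 × 0.3 = 0.688
- p = 0.2, k = 3: 0.640 + 0.128/1.7 + 0.032 × 0.3 = 0.725
- p = 0.1, k = 2: 0.810 + 0.09 × 0.3 = 0.837
- p = 0.1, k = 3: 0.810 + 0.081/1.7 + 0.009 × 0.3 = 0.860

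| Skipped | Phases entered | Classical ANOVA | Paired t-test | Mixed model |
|---|---|---|---|---|
| 20% | 2 | 64% | 64% | 69% |
| 20% | 3 | 51% | 64% | 73% |
| 10% | 2 | 81% | 81% | 84% |
| 10% | 3 | 73% | 81% | 86% |

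For r from 0.8 to 0.5 at 20% skipped, the mixed model gives 67% to 72% (two phases) and 72% to 74% (three). If skipping clusters within people (intraclass correlation 0.3, 20% skipped, r = 0.7), the ANOVA and mixed-model shares are 69% and 72% (two phases), 61% and 74% (three).

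**Step 3: bias within one group.** Assume SD 1, no true change, two visits, r = 0.7, and Phase 5 skipped with probability 0.4 when a driving value is below its mean, so 20% are skipped. The mean of a standard normal above zero is 0.798. Among those observed, the driver's mean is (0.5 × 0.798 − 0.5 × 0.6 × 0.798)/0.8 = 0.1995, and its variance is 1 − 0.1995² = 0.960.
- *Driver is the observed Phase 3 value.* Phase 5 mean off by 0.7 × 0.20 = 0.14; complete-case change off by 0.14 − 0.20 = −0.06; mixed model 0.00.
- *Driver is the unseen Phase 5 value.* Phase 5 mean off by 0.20; complete-case change 0.20 − 0.14 = 0.06. The mixed model uses the completers' slope, 0.7 × 0.960/(1 − 0.49 × 0.040) = 0.685, and is off by 0.1995 − 0.685 × 0.140 = 0.10.
- *Driver is the unseen change.* Its SD is √(2 − 1.4) = 0.775, so the complete-case change is off by 0.1995 × 0.775 = 0.15. Completers' means are −0.077 and +0.077, and their slope is (0.85 − 0.15 × 0.960)/(0.85 + 0.15 × 0.960) = 0.71. The mixed model is off by 0.077 + 0.71 × 0.077 = 0.13.

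The last two cases rank the methods in opposite order, and the order within each case is the same at r = 0.5 and r = 0.8.

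**Step 4: bias in the group difference.** Simulation with the same skipping rule in both groups, r = 0.7 and an assumed treatment effect of 0.5 SD:
- Phase 3 value as driver: 0.00 for complete cases, mixed model and Phase 5 t-test.
- Phase 5 value as driver: −0.01 (complete cases), −0.02 (mixed model), −0.04 SD (Phase 5 t-test).

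**The case against.** The strongest reply is that this is a proof-of-concept pilot with tentatively worded analyses, that the form of ANOVA is not named, and that an all-available-data model may already be meant. If so, nothing is lost and one sentence settles it. The gain is also small in the only case where the documents fix the phases, DXA and CT: 64% to 69%, or 81% to 84%, under assumed skip rates. The larger gain needs three phases in one ANOVA, which the plan never states. These points stand, and they set the severity.

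Three stronger readings are tempting and are not supported.
- *Omission related to function biases the comparison.* Step 4 shows that this is not enough: under a common rule the bias largely cancels. Material bias also needs the omission to differ between groups. The documents tie omission to scheduling and give no sign of such a difference, though they do not exclude it.
- *A mixed model cures selective omission, or is always worse than complete cases when omission depends on unseen values.* Step 3 contradicts both.
- *The omission note contradicts the treadmill section, because skipping the earlier test leaves the Phase 3 submaximal test without a stated end point.* The discretion to omit covers the submaximal test as well. This is a contingency left unaddressed, not a contradiction, and it is separate from the analysis question.

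**Conclusion.** The gap is real and minor. The protocol foresees partly observed participants, and the analysis section has no rule for them. If the named methods are applied in classical form, data already collected are discarded. Under the assumed correlation of 0.7, the effective share for the Phase 3-to-5 change falls short of a mixed model by 3 to 5 percentage points if two phases enter (84 − 81 and 69 − 64) and by 13 to 22 if three enter (86 − 73 and 73 − 51), at 10% and 20% skipped. These sizes rest on assumed skip rates, correlation and number of phases, and on equal correlations between visits; none comes from the documents.

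The point concerns precision first. Bias in the group comparison remains a possibility only. A mixed model removes it only when omission depends on values already observed. It does not recover an outcome skipped at every visit.

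**What to change.** In STATISTICAL ANALYSIS, replace repeated measures ANOVA with a likelihood-based mixed model for repeated measures: group, phase and group-by-phase terms, REML, and small-sample degrees of freedom. It should use all available measurements at the phases scheduled in all groups compared, with those phases named for each outcome. If this is what repeated measures ANOVA was meant to be, say so.

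Report, by group and phase, the number analysed for each outcome and the tests omitted with reasons. The research notes already required record the omissions; the reason should be entered with each.

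A sensitivity analysis for omission related to unseen values is optional. It should be limited to the functional outcomes, because a shift towards worse has no clear direction for biomarkers or body composition and no main outcome is designated.

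The cost is a few sentences and slightly more analysis work. Visits and scheduling flexibility are unchanged.

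### Does allowing strength to be tested on either of two devices, with no written same-device rule, undermine the strength change scores?

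*Combined protocol and SAP*

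**What the plan says.** The Strength Testing item under TESTING PROCEDURES has two parts. In part A, strength on up to three leg movements "will be measured by 1-repetition maximum (1RM) testing on Keiser K-300 air powered machines or a Biodex strength testing system". In part B, "Plantar and dorsiflexion will be measured using a hand-held dynamometer or with the Biodex strength testing system". The item describes warm-up, number of trials, rest, stabilization and encouragement. It does not say how a device is chosen or whether a participant keeps it.

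The opening note of TESTING PROCEDURES lets the team omit procedures and says of that case: "If this occurs it will be noted in the participant research notes". It also allows retesting: "Participants may also be asked to repeat one or more of the research tests should it be necessary due to a technical error", among other measurement problems. Neither provision mentions the device.

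Under STATISTICAL ANALYSIS, "our intent is to use repeated measures ANOVA to compare outcome measures among treatment and control", but as this is a pilot "we may initially analyze within-group changes using paired t-tests and among-group differences with independent samples t-tests". The pilot is also meant "to generate data with which to make accurate power calculations". Data are to be screened, "looking for extreme values which will be checked for transcription or other errors". No device term or mixed-device rule appears.

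**The concern.** Readings from two strength-testing devices need not agree. If a participant is tested on one device before the intervention and on another afterwards, the difference between visits includes the offset between devices. Three consequences would follow:

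- The SD of change is inflated, and with it any sample size later planned from it. That bears directly on the pilot's stated purpose.
- If switches run mainly one way, the within-group paired t-test is biased, even when both groups switch equally.
- If switches are concentrated in one group, the between-group contrast is biased as well.

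Screening for extreme values would miss most moderate offsets. If the device were not recorded, the affected changes could not be identified at analysis.

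**Working it through.** **What can be checked.** The document gives no device offset, switching rate, retest correlation, SD, alpha or group size, so there is no figure of the plan's own to reproduce. Every input below is an assumption: 15 per group, retest correlation r = 0.8, a constant offset d in units of the within-device SD, and two-sided 5% tests. Rejection rates come from 200,000 simulated trials per setting. The SD of a same-device change is √(2(1−r)) = √0.4 = 0.632.

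**1. No one switches.** Change scores contain no offset. If devices differ only between participants, a constant offset cancels from each person's change. Only pooled raw values are affected: their variance is multiplied by 1 + p(1−p)d², where p is the share on the second device. For d = 1 this is 1.188 at p = 0.25 and 1.25 at p = 0.5, so the raw SD rises 9–12%.

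**2. SD of change, one-way switching by a share s.** Variance ratio = 1 + s(1−s)d² / (2(1−r)).
- d = 1, s = 0.1: 1 + 0.09/0.4 = 1.225, SD up 11%.
- d = 1, s = 0.2: 1 + 0.16/0.4 = 1.40, SD up 18%.
- d = 0.5, s = 0.1 and 0.2: 1.056 and 1.10, SD up 3% and 5%.

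A sample size planned from the inflated SD rises by the variance ratio: 22.5–40% at d = 1, and about 6–10% at d = 0.5.

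**3. Paired t-test, no true change, n = 15.**

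| Switching pattern | d | Rejection rate |
|---|---|---|
| 3 one way | 0.5 | 7.4% |
| 3 one way | 1 | 12% |
| 3 one way | 2 | 18% |
| 2 one way | 1 | 7.4% |
| 1 only | 1 | about 5% (no excess) |
| 2 up, 1 down | 1 | 2.6% |

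Error is inflated only when switching is mostly one way and involves at least 2 of 15. In the last row the SD still rises: the offset variance is 3/15 − (1/15)² = 0.196, and the ratio is 1 + 0.196/0.4 = 1.49, so the SD is up 22%.

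**4. Between groups, 15 v 15, d = 1.**
- 3 v 0 switching: false difference (3/15)/0.632 = 0.32 change SDs, about 9.5% rejection.
- 3 v 1: (2/15)/0.632 = 0.21 change SDs, about 5.1%.
- 3 v 3: no bias, about 2%.
- Each participant switching at random with probability 0.2 in both groups: 5.0%.

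**5. Would excluding mixed changes help?** A true effect of 1.06 change SDs gives 80% power at 15 v 15. Dropping 3 per group (12 v 12) gives 70%. Leaving 3 v 3 mixed changes in gives:

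| d | Power, left in | Power, excluded |
|---|---|---|
| 0.5 | 77% | 70% |
| 1 | 67% | 70% |
| 2 | 33% | 70% |

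Exclusion loses 7 points, gains about 3, or gains 37, depending on an unknown offset. A device factor in the change-score model gains nothing when each participant stays on one device and the offset is constant, because step 1 shows that the offset has already cancelled.

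**6. Would screening catch a switch?** With an assumed flag at 3 change SDs and d = 1, P(Z > 3 − 1/0.632) = P(Z > 1.42) = 7.8%. Screening alone is a weak safeguard.

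**The case for a change.** The strongest case for acting is that both device choices are unqualified and that the protocol builds in flexible conduct around each participant's availability. The protocol also shows that it can write a cross-phase comparability rule: in Phases 3 and 5 the submaximal treadmill test stops at the time and grade reached in an earlier phase. Strength Testing has no counterpart, although a same-device sentence would suit its level of detail and cost almost nothing. Which device is used is settled at the test visit, and an unrecorded switch cannot be repaired afterwards.

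Much of this stands. The wording does permit a switch, no recording rule is written, and the arithmetic is right given its inputs. It does not show that the plan leads a competent team astray. Permission to use either machine is not a plan to move people between machines. Testing the same person the same way at each visit is ordinary practice, and the provision for retesting after a measurement problem could cover a test done on the wrong machine. Test forms are not part of the document and may well record the device, so failure to record it is not shown. The treadmill rule defines when a separate test ends, so its presence does not imply that other tests will be done inconsistently.

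**Conclusion.** No change follows. The gap is a detail left to test conduct, and staff fill it correctly by keeping each participant on one device, which the plan fully allows. In that case the change scores are unaffected, as are the paired tests and the SDs of change carried into later power calculations.

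The harm depends on switching that the document permits but never describes. For an offset of 1 within-device SD, inflation of the paired test's error needs mainly one-way switching by 2 or more of 15 participants, which gives 7.4% and upwards. Between groups it needs switching confined largely to one arm. Inflation of the SD of change needs only that some participants switch. It is 3–5% for a 0.5 SD offset and 11–18% for a 1 SD offset when 10–20% switch one way, and somewhat more if switches go both ways. All these figures rest on assumed offsets, rates, correlation and group size.

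The consequence is limited in any case: no outcome is named as primary, strength is one of many, and the study is a proof-of-concept pilot. Adding device rules to the analysis is not clearly better, since mandatory exclusion costs power at small offsets and a device factor gains nothing when nobody switches. If a switch did come to light, an analyst could count such changes by group and repeat the strength analysis without them, and nothing in the plan prevents that.

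### Item 3B lets maximal plantarflexion be measured with an unfixed hand-held dynamometer, so a tester-strength ceiling may hide part of a true gain; the size is unknown and the fix is cheap

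*Combined protocol and SAP*

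**What the plan says.** In the Combined protocol and SAP, TESTING PROCEDURES, item 3 (Strength Testing), part B offers two devices for both ankle movements: "Plantar and dorsiflexion will be measured using a hand-held dynamometer or with the Biodex strength testing system". It gives no rule for choosing between them and no requirement to keep one device for a participant across visits. On set-up it says: "Participants will be properly stabilized to ensure minimal movement artifacts". That concerns the participant; how the dynamometer is held is not described. The effort is meant to be maximal: "verbal encouragement will be provided during task to encourage maximal volitional contraction".

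The plantarflexors are a target of both interventions. NMES is used to "electrically induce contraction of the plantarflexors and dorsiflexors of both lower extremities". The strength component of active training, which is optional, is described thus: "This will consist of training of the knee extensors, knee flexors, plantar flexors and dorsiflexors".

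For analysis, the STATISTICAL ANALYSIS section says "our intent is to use repeated measures ANOVA to compare outcome measures among treatment and control", with t-tests as a possible first step. Extreme values are checked for errors. Readings limited by the instrument or the tester are not mentioned.

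**The concern.** A dynamometer pressed against the foot by a tester measures the participant's maximal force only while the tester can hold it still. Above that point it records what the tester can resist, and a participant already there at baseline cannot show a gain. Stabilising the participant does not raise the tester's limit. Using the same tester-held device throughout does not remove it either.

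The planned analysis would not reveal the problem. Capped readings bunch together instead of standing out, so a check for extreme values passes over them, and ANOVA or t-tests take them at face value. Both the mean change and the SD would be pulled down, and tester strength would enter the score. This matters because the SAP describes the trial's purpose in these words: "this is a pilot study designed to demonstrate proof of concept and to generate data with which to make accurate power calculations". A gain and an SD that are both too small are poor inputs for that purpose.

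**Working it through.** The documents give no plantarflexion force, SD, expected gain, tester limit, sample size or power, so there is no figure of the plan's own to reproduce. What follows is an illustration on assumed inputs.

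**Assumptions (none from the documents)**
- True baseline force is normal with mean m = 150, 200, 250, 300, 450 or 600 N and SD s = 0.30m.
- Each participant's true force rises by 15%, so the later mean is 1.15m and the later SD 1.15s.
- A tester-held reading is min(true force, c), with tester limit c = 250, 300 or 400 N.

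**Formulas.** With a = (c − m)/s, the mean reading is

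E[min(X, c)] = mΦ(a) − sφ(a) + c(1 − Φ(a)).

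The recorded share of the gain is f = (mean reading after − mean reading before) / (0.15m). If a random half of participants are tested on the Biodex with no cap, the share is 0.5 + 0.5f.

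**One cell in full: m = 450 N, s = 135 N, c = 300 N**
- Before: a = −1.111, Φ = 0.1333, φ = 0.2152. Mean reading = 59.97 − 29.05 + 260.02 = 290.9 N. Share already at the limit = 1 − 0.1333 = 87%.
- After: mean 517.5, SD 155.25, a = −1.401, Φ = 0.0806, φ = 0.1495. Mean reading = 41.72 − 23.21 + 275.82 = 294.3 N.
- Recorded gain = 3.38 N against a true 67.5 N, so f = 3.38/67.5 = 5%.
- SD of the later readings: E[min²] = (m² + s²)Φ − s(m + c)φ + c²(1 − Φ), taken at the later mean and SD, gives 26 N instead of 155 N. Mean gain over later SD falls from 67.5/155.25 = 0.43 to 3.38/26 = 0.13, so the smaller SD does not make up for the lost gain.

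**All cells: share of the true gain recorded, everyone tested by hand (in brackets: half on the Biodex)**

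| Mean true force | Limit 250 N | Limit 300 N | Limit 400 N |
|---|---|---|---|
| 150 N | 94% (97%) | >99% (>99%) | 100% (100%) |
| 200 N | 60% (80%) | 85% (93%) | >99% (>99%) |
| 250 N | 29% (65%) | 54% (77%) | 91% (96%) |
| 300 N | 14% (57%) | 29% (65%) | 70% (85%) |
| 450 N | 2% (51%) | 5% (53%) | 18% (59%) |
| 600 N | 1% (50%) | 1% (51%) | 5% (53%) |

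With everyone tested by hand, 9 of the 18 cells record less than half of the gain and 9 record more. The count carries no probability, since the grid is assumed. It does show what drives the loss: where the limit lies at or below the mean true force, at most 29% is recorded; where it lies well above, almost nothing is lost.

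The same pattern appears without any newtons. With a normal baseline, a uniform gain of 0.25 to 1.0 SD and everyone tested by hand, a limit 1 SD below the baseline mean leaves 7–13% recorded, a limit at the mean 32–45%, 1 SD above 68–81%, and 2 SD above 93–97%.

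**The case against.** A reader might infer that a plantarflexion gain would go largely unrecorded. The documents do not support that. It needs a tester limit at or below about the average participant's strength and mostly hand-held testing, and neither is stated. The participants are Veterans with PAD after revascularization and may be weak. The load of a single-leg heel raise, about one body weight (70 kg × 9.81 = 687 N), may suggest forces no tester could hold, but nothing in the plan says these participants can perform one.

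Three further points count on the other side. The Biodex is named in the same sentence and has no tester limit. Tester-held use is the ordinary meaning of a hand-held device but is still an inference, because a strap or frame is not forbidden. And the reach is small: plantarflexion is half of one sub-item in a long battery, any procedure may be skipped, strength training is optional, and the leg extension, leg press and leg flexion tests of item 3A use Keiser machines or the Biodex. It would therefore also be wrong to infer that the pilot as a whole could miss a strength effect for this reason.

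These points limit the size and importance of the concern. They do not remove it: hand-held testing of every participant at every visit would comply with the plan, and nothing in the plan would prevent or detect a ceiling.

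**Conclusion.** The point holds as a risk of unknown size on one measure. Item 3B permits a method that, if the device is held by the tester, cannot record force above the tester's own limit, in a muscle group that NMES and the optional strength training target. Under the assumptions stated, the recorded share of a 15% gain runs from about 1% to 100% with all hand-held testing, and is at least 50% if half of the participants, chosen without regard to strength, are tested on the Biodex. The SD can shrink along with the gain. The documents do not settle where in that range this trial lies. Only plantarflexion strength is affected, and it is not named as a primary outcome. This is a minor, cheap improvement.

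**What to change.** Reword item 3B along these lines: *Plantarflexion strength will be measured on the Biodex system or, when it cannot be used, with a dynamometer held by a strap or fixed frame. Each participant will be tested with the same device at all visits, and the device used will be recorded. A tester-held dynamometer may be used for dorsiflexion only.*

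Keeping one device per participant also stops a change of device from being read as a change in strength. Consistency alone is not enough, because a tester-held device used at every visit keeps the ceiling.

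The change is a few sentences, and the Biodex is already named for this test. The cost is slightly more set-up time and some missing plantarflexion values when neither the Biodex nor a fixed dynamometer can be used. The documents do not say how often that would happen. Missing values would at least be visible, whereas capped ones are not.
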